		of administration is intravenous for an intravenous anti-infective (dichotomous)	
1	Neutropenia	Medical claim with an ICD-10 code in the inpatient or non-IP setting for neutropenia (dichotomous)	MM diagnosis to 1 day prior to index date
1	Hypercalcemia	Medical claim with an ICD-10 code in the inpatient or non-IP setting for hypercalcemia (dichotomous)	MM diagnosis to 1 day prior to index date
1	Hepatotoxicity	Medical claim with an ICD-10 code in the inpatient or non-IP setting for hepatotoxicity (dichotomous)	MM diagnosis to 1 day prior to index date
1	Renal failure	Medical claim with an ICD-10 code in the inpatient or non-IP setting for renal failure (dichotomous)	MM diagnosis to 1 day prior to index date
1	Amyloidosis	Medical claim with an ICD-10 code in the inpatient or non-IP setting for amyloidosis (dichotomous)	MM diagnosis to 1 day prior to index date
1	Hypertension	Medical claim with an ICD-10 code in the inpatient or non-IP setting for hypertension (dichotomous)	MM diagnosis to 1 day prior to index date
1	Extramedullary disease	Medical claim with an ICD-10 code in the inpatient or non-IP setting for extramedullary disease (dichotomous)	MM diagnosis to 1 day prior to index date
1	Charlson Comorbidity Index (CCI) score	CCI ¹⁸ (continuous and categorical): • 0 (no comorbidities) • 1 to 2 (mild) • 3 to 4 (moderate) • ≥ 5 (severe)	180 days prior to index date to index
1	Myocardial infarction	Medical claim with an ICD-10 code in the inpatient or non-IP setting for myocardial infarction (dichotomous)	180 days prior to index date to index
1	Congestive heart failure	Medical claim with an ICD-10 code in the inpatient or non-IP setting for congestive heart failure (dichotomous)	180 days prior to index date to index date

Objective	Variable	Definition	Assessment Period(s)
1	Peripheral vascular disease	Medical claim with an ICD-10 code in the inpatient or non-IP setting for peripheral vascular disease (dichotomous)	180 days prior to index date to index
1	Cerebrovascular disease	Medical claim with an ICD-10 code in the inpatient or non-IP setting for cerebrovascular disease (dichotomous)	180 days prior to index date to index
1	Dementia	Medical claim with an ICD-10 code in the inpatient or non-IP setting for dementia (dichotomous)	180 days prior to index date to index
1	Chronic pulmonary disease	Medical claim with an ICD-10 code in the inpatient or non-IP setting for chronic pulmonary disease (dichotomous)	180 days prior to index date to index

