Exploratory Obj 1	Hypogammaglobuli nemia ¹	Medical claim with an ICD-10 code in the inpatient, non-IP, or pharmacy setting for hypogammaglobulinemia (dichotomous)	Index date to end of follow-up, where follow-up will be based on last dose of elranatamab or teclistamab (e.g., 14 days after last recorded dose or 90 days after last recorded dose).
Exploratory Obj 1	Hypophosphataemia	Medical claim with an ICD-10 code in the inpatient, non-IP, or pharmacy setting for hypophosphatemia (dichotomous)	Index date to end of follow-up, where follow-up will be based on last dose of elranatamab or teclistamab (e.g., 14 days after last recorded dose or 90 days after last recorded dose).
Exploratory Obj 1	Hypokalaemia ¹	Medical claim with an ICD-10 code in the inpatient, non-IP, or pharmacy setting for hypokalemia (dichotomous)	Index date to end of follow-up, where follow-up will be based on last dose of elranatamab or teclistamab (e.g., 14 days after last recorded dose or 90 days after last recorded dose).
Exploratory Obj 1	Hepatotoxicity ¹	Medical claim with an ICD-10 code in the inpatient, non-IP, or pharmacy setting for hepatotoxicity (dichotomous)	Index date to end of follow-up, where follow- up will be based on last dose of elranatamab or teclistamab (e.g., 14 days after last recorded dose or

			90 days after last recorded dose).
Exploratory Obj 1	Renal failure ²	Medical claim with an ICD-10 code in the inpatient, non-IP, or pharmacy setting for renal failure (dichotomous)	Index date to end of follow-up, where follow-up will be based on last dose of elranatamab or teclistamab (e.g., 14 days after last recorded dose or 90 days after last recorded dose).
Exploratory Obj 1	Peripheral neuropathy ¹	Medical claim with an ICD-10 code in the inpatient, non-IP, or pharmacy setting for peripheral neuropathy (dichotomous)	Index date to end of follow-up, where follow-up will be based on last dose of elranatamab or teclistamab (e.g., 14 days after last recorded dose or 90 days after last recorded dose).
Exploratory Obj 1	Arthralgia ³	Medical claim with an ICD-10 code in the inpatient, non-IP, or pharmacy setting for arthralgia (dichotomous)	Index date to end of follow-up, where follow-up will be based on last dose of elranatamab or teclistamab (e.g., 14 days after last recorded dose or 90 days after last recorded dose).

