Exploratory Obj 1	Other infectious hepatitis ²	Medical claim with an ICD-10 code in the inpatient, non-IP or pharmacy setting for infectious hepatitis (other than hepatitis B or C) (dichotomous)	Index date to end of follow-up, where follow-up will be based on last dose of elranatamab or teclistamab (e.g., 14 days after last recorded dose or 90 days after last recorded dose).
Exploratory Obj 1	Helicobacter pylori ²	Medical claim with an ICD-10 code in the inpatient, non-IP or pharmacy setting for helicobacter pylori (dichotomous)	Index date to end of follow-up, where follow-up will be based on last dose of elranatamab or teclistamab (e.g., 14 days after last recorded dose or 90 days after last recorded dose).

Exploratory Obj 1	Candida esophagitis ²	Medical claim with an ICD-10 code in the inpatient, non-IP or pharmacy setting for candida esophagitis (dichotomous)	Index date to end of follow-up, where follow-up will be based on last dose of elranatamab or teclistamab (e.g., 14 days after last recorded dose or 90 days after last recorded dose).				
Exploratory Obj 1	Urinary tract infection ²	Medical claim with an ICD-10 code in the inpatient, non-IP or pharmacy setting for a urinary tract infection (dichotomous)	Index date to end of follow-up, where follow-up will be based on last dose of elranatamab or teclistamab (e.g., 14 days after last recorded dose or 90 days after last recorded dose).				
Exploratory Obj 1	Time to infection onset	Time in days from index date to first infection for the following infections:	Index date until censor				
Effectiveness	Effectiveness						
Exploratory Obj 2	os	Time (in months) from index date until date of death (continuous)	Index date until censor				
Exploratory Obj 2	TTNT/D	Time (in months) from index date until the date of the next treatment (CAR-T, BsABs, bendamustine or belantamab) or death (continuous)	Index date until censor				

- 1. Variable will be measured as incident and prevalent. Incident cases have 30-day washout period applied
- 2. Variable will be measured as incident and prevalent. Incident cases have 60-day washout period applied
- 3. Variable will be measured as incident and prevalent. Incident cases have 14-day washout period applied

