9.7.6. Tolerability

The prevalence and incidence for each adverse event (Table 3) will be estimated. All prevalence and incidence estimates will be reported as a percent with corresponding 95% CIs.

Prevalance =
$$(\frac{No.\ of\ patients\ with\ an\ event}{Total\ number\ of\ patients\ in\ the\ cohort})\ x\ 100$$

For the incidence analysis, only patients who did not have the event prior to their index date will be included. The length of the washout is dependent on the outcome (see Table 3).

$$Incidence = \left(\frac{\text{No. of patients with an event that did not have an event in baseline}}{\text{Total number of patients in the cohort}}\right) x \ 100$$

PFIZER CONFIDENTIAL

Patients will be assessed over two time periods: from the index date until 14 days or 90 days after their last administration of the index medication.

Additionally, the time to infection onset will be assessed using unadjusted Kaplan-Meier methods. The median time to event in days will be reported along with the IQR. The 95% CIs for the median time to event will be calculated using log-log transformation.

Patients will be censored at the earliest of death, next treatment (CAR-T, BsABs, bendamustine or belantamab), the end of part A or B continuous closed-claim coverage, or the end of data.

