	Clinical, Adverse event		E13.41, G57.70, G57.71, G57.72, G57.73, G59, G57.80, G57.81, G57.82, G57.83, G58.8, G58.9, G64., G61.0, M05.50, M05.511, M05.512, M05.519, M05.521, M05.522, M05.529, M05.531, M05.532, M05.539, M05.541, M05.542, M05.549, M05.551, M05.552, M05.559, M05.551, M05.552, M05.559, M05.571, M05.572, M05.579, M05.59, E08.40, E08.42, E09.40, E09.42, E10.40, E10.42, E11.40, E11.42, E13.40, E13.42, G13.0, G13.1, A36.83, A52.15, G63, M34.83, G62.1, G61.1, G62.0, G62.2, G62.82, G61.81, G62.81, G61.89, G62.89, G61.9, G62.9, H46.3, M54.10, M54.18, M79.2, R20.0, R20.1, R20.2, R20.3, R20.8, R20.9
Any infection	Baseline characteristic - Clinical	Claims data	An ICD-10 Diagnosis Code for any of the following types of infections. See the rows below for codes for each infection type. COVID-19, Adenoviral pneumonia, Cytomegaloviral pneumonitis, Other Pneumonia, Upper respiratory tract infection, Sepsis, Cytomegaloviral infection, Pneumocystis jiroveci pneumonia (PJP), Hepatitis C, Hepatitis B, Other infectious hepatitis, Helicobacter pylori, Candida esophagitis, Urinary tract infection
Use of intravenous anti- infective	Baseline characteristic - Clinical	Claims data	See "Antivirals" and "Antibiotics" above
Neutropenia	Baseline characteristic - Clinical, Adverse event	Claims data	ICD-10 Diagnosis: D70x
Hypercalcemia	Baseline characteristic - Clinical	Claims data	ICD-10 Diagnosis: E83.52
Hypoxia	Baseline characteristic - Clinical, Adverse event	Claims data	ICD-10 Diagnosis: J96.20, J96.11, J96.90, J96.01, J96.00, J96.10, J96.21, J96.91, I27.23, R09.02
Hepatotoxicity	Baseline characteristic - Clinical, Adverse event	Claims data	ICD-10 Diagnosis: K71.x
Renal failure	Baseline characteristic -	Claims data	ICD-10 Diagnosis: N17x, N18x, N19x, R34x, T82.4, Z49.02, Z99.2

	Clinical, Adverse event		
Amyloidosis	Baseline characteristic - Clinical	Claims data	ICD-10 Diagnosis: E85.4x, E85.8x, E85.9x
Hypertension	Baseline characteristic - Clinical	Claims data	ICD-10 Diagnosis: I10x-I15x, I16x
Extramedullary disease	Baseline characteristic - Clinical	Claims data	ICD-10 Diagnosis: C90.2x
CCI score	Baseline characteristic - Clinical	Claims data	See components below
Myocardial infarction	Baseline characteristic - Clinical	Claims data	ICD-10 Diagnosis: I21.x, I22.x, I25.2
Congestive heart failure	Baseline characteristic - Clinical	Claims data	ICD-10 Diagnosis: I11.0, I13.0, I13.2, I25.5, I42.0, I42.5, I42.6, I42.7, I42.8, I42.9, I43.x, I50.x, P29.0

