Peripheral vascular disease	Baseline characteristic - Clinical	Claims data	ICD-10 Diagnosis: I70.x, I71.x, I73.1, I73.8, I73.9, I77.1, I79.0, I79.1, I79.8, K55.1, K55.8, K55.9, Z95.8, Z95.9
Cerebrovascular disease	Baseline characteristic - Clinical	Claims data	ICD-10 Diagnosis: G45.x, G46.x, H34.0x, H34.1x, H34.2x, I60.x, I61.x, I62.x, I63.x, I64.x, I65.x, I66.x, I67.x, I68.x
Dementia	Baseline characteristic - Clinical	Claims data	ICD-10 Diagnosis: F01.x, F02.x, F03.x, F04, F05, F06.1, F06.8, G13.2, G13.8, G30.x, G31.0x, G31.1, G31.2, G91.4, G94, R41.81, R54
Chronic pulmonary disease	Baseline characteristic - Clinical	Claims data	ICD-10 Diagnosis: J40.x, J41.x, J42.x, J43.x, J44.x, J45.x, J46.x, J47.x, J60.x, J61.x, J62.x, J63.x, J64.x, J65.x, J66.x, J67.x, J68.4, J70.1, J70.3
Rheumatic disease	Baseline characteristic - Clinical	Claims data	ICD-10 Diagnosis: M05.x, M06.x, M31.5, M32.x, M33.x, M34.x, M35.1, M35.3, M36.0
Peptic ulcer disease	Baseline characteristic - Clinical	Claims data	ICD-10 Diagnosis: K25.x, K26.x, K27.x, K28.x

Liver disease	Baseline characteristic - Clinical	Claims data	ICD-10 Diagnosis: B18.x, K70.0, K70.1, K70.2, K70.3, K70.9, K71.3, K71.4, K71.5, K71.7, K73.x, K74.x, K76.0, K76.2, K76.3, K76.4, K76.8, K76.9, Z94.4, I85.0x, I86.4, K70.4x, K71.1x, K72.1x, K72.9x, K76.5, K76.6, K76.7
Diabetes	Baseline characteristic - Clinical	Claims data	ICD-10 Diagnosis: E08.0x, E08.1x, E08.6x, E08.8x, E08.9x, E09.0x, E09.1x, E09.6x, E09.8x, E09.9x, E10.0x, E10.1x, E10.6x, E10.8x, E10.9x, E11.0x, E11.1x, E11.6x, E11.8x, E11.9x, E13.0x, E13.1x, E13.6x, E13.8x, E13.9x, E08.2x, E08.3x, E08.4x, E08.5x, E09.2x, E09.3x, E09.4x, E09.5x, E10.2x, E10.3x, E10.4x, E10.5x, E11.2x, E11.3x, E11.4x, E11.5x, E13.2x, E13.3x, E13.4x, E13.5x
Renal disease	Baseline characteristic - Clinical	Claims data	ICD-10 Diagnosis: I12.9, I13.0, I13.10, N03.x, N05.x, N18.1, N18.2, N18.3, N18.4, N18.9, Z94.0, I12.0, I13.11, I13.2, N18.5, N18.6, N19.x, N25.0, Z49.x, Z99.2
Hemiplegia or paraplegia	Baseline characteristic - Clinical	Claims data	ICD-10 Diagnosis: G04.1, G11.4, G80.0, G80.1, G80.2, G81.x, G82.x, G83.x
Human immunodeficiency virus	Baseline characteristic - Clinical	Claims data	ICD-10 Diagnosis: B20.x
Metastatic solid tumor	Baseline characteristic - Clinical	Claims data	ICD-10 Diagnosis: C77.x, C78.x, C79.x, C80.0, C80.2

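### The Renal failure code list takes in all of N18 and the dialysis codes, so the prevalent adverse event counts stable chronic kidney disease as renal failure on treatment

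*Protocol*

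**What the plan says.** - **Adverse event.** Protocol Section 9.3, Table 3 counts a "Medical claim with an ICD-10 code in the inpatient, non-IP, or pharmacy setting for renal failure (dichotomous", from the index date to 14 or 90 days after the last dose. It sets no condition on stage, acuity or new onset.
- **Baseline variable.** Table 2 counts a "Medical claim with an ICD-10 code in the inpatient or non-IP setting for renal failure (dichotomous", from MM diagnosis to the day before index.
- **Codes.** Annex 2 has one Renal failure row for both roles: "ICD-10 Diagnosis: N17x, N18x, N19x, R34x, T82.4, Z49.02, Z99.2". N18 carries a wildcard and no stage limit.
- **A second renal variable.** Annex 2 also defines Renal disease, a Charlson component, whose list begins "I12.9, I13.0, I13.10, N03.x, N05.x, N18.1, N18.2, N18.3, N18.4, N18.9, Z94.0" and goes on to N18.5, N18.6, N19.x, Z49.x and Z99.2. It is a baseline variable only, measured in the 180 days before index (Table 2).
- **Measures.** Section 9.7.6: "The prevalence and incidence for each adverse event (Table 3) will be estimated". The Table 3 footnote for renal failure reads "Variable will be measured as incident and prevalent. Incident cases have 60-day washout period applied". The washout therefore applies to the incident measure alone.
- **Binding force.** Section 9.8 says that outcomes will be coded from the protocol's own codes and that the protocol will be strictly followed.

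**The concern.** The row is labelled renal failure and reported under tolerability and safety, but its codes also capture long-standing kidney disease that predates the drug. Section 7 names renal failure as a feature of myeloma, and Section 9.9 expects an older cohort with a higher disease burden, so such codes should be common. One routine visit after index at which the chronic diagnosis is coded is enough for an event.

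At stake is whether the renal safety percentage, produced separately for elranatamab and teclistamab, says anything about renal events after treatment starts or mainly describes comorbidity at entry. Section 9.7 also plans a subgroup of beneficiaries entitled through ESRD. With N18.6 and Z99.2 in the list, these patients meet the prevalent event almost by construction.

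**Working it through.** The protocol states no renal rate, so there is no figure to reproduce. The check is a comparison of code lists followed by an illustration of size.

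**1. The two lists.**
- In Renal failure and also in Renal disease: N18.1 to N18.6, N18.9, N19, Z99.2, and Z49.02 (through Z49.x).
- In Renal failure only: N17x, R34x, T82.4.

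Every N18 code listed for the chronic comorbidity therefore also triggers the adverse event.

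**2. Prevalence (Section 9.7.6).** This is patients with an event divided by all patients in the cohort, with no washout. A patient with chronic disease for years and one N18 claim in the window adds 1 to the numerator.

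**3. Size of the effect on prevalence.** Assumptions, none from the protocol: a share C = 30–50% has a non-end-stage N18 code in the window, a share A = 10–20% has acute or end-stage failure, and the two are independent. Prevalence as coded = 1 − (1 − C)(1 − A).
- C 30%, A 10%: 1 − 0.70 × 0.90 = 0.37; ratio 0.37/0.10 = 3.7
- C 30%, A 20%: 1 − 0.70 × 0.80 = 0.44; ratio 0.44/0.20 = 2.2
- C 50%, A 10%: 1 − 0.50 × 0.90 = 0.55; ratio 0.55/0.10 = 5.5
- C 50%, A 20%: 1 − 0.50 × 0.80 = 0.60; ratio 0.60/0.20 = 3.0

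The result is 37–60% against 10–20%, a ratio of 2.2 to 5.5. A lower set (C 20–40%, A 5–20%) gives 24–52% against 5–20%. With n = 133, the August 2024 claim count in Section 9.5, used only for scale, the case C 30%, A 10% gives 37.0% (Wilson 95% CI 29.3–45.5) against 10.0% (6.0–16.3).

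**4. Incidence.** Assume that chronic-disease claims arrive at a constant rate r per 30 days, with f months of follow-up. A stable chronic patient becomes a false new case if nothing is coded in the 60-day washout and something is coded afterwards: exp(−2r) × (1 − exp(−rf)).
- r = 0.25, f = 6: 0.6065 × 0.7769 = 0.47
- r = 1.0, f = 3: 0.1353 × 0.9502 = 0.13

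For r from 0.25 to 1.0 and f from 3 to 6, between 13% and 47% of stable chronic patients enter as false incident cases. With C = 30–50%, that is 0.1286 × 0.30 = 3.9% to 0.4712 × 0.50 = 23.6% of the cohort. Conversely, 1 − exp(−2r) = 39–86% of chronic patients are removed by the washout, and any true N17 event they later have is lost with them.

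**The case against.** **Prevalence is meant to include existing disease.** New onset is the separate incidence measure, and 60 days is the longest of the three washouts in Table 3. This stands in part. A reader might infer that no renal result can be used. The documents do not support that, because the washout does exclude recently coded chronic patients. It does not exclude those coded less often, and it also discards acute events in the patients it removes.

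**Overlap does not prove a mistake.** A reader might infer that the protocol contradicts itself because the same codes sit under two names. It does not. Charlson components overlap other variables elsewhere in Annex 2 (K71 codes under both Hepatotoxicity and Liver disease), the run N17x–N18x–N19x may be deliberate, and the protocol never calls the event acute. The fault is that a chronic category is counted as an on-treatment event under this label. For the liver, by contrast, B18, K70, K73 and K74 stay out of the adverse event.

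**The baseline row is defensible.** Section 9.2 gives MM-related comorbidities the window from MM diagnosis, and chronic codes are plausible there. This stands: the baseline issue is one of label.

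**The stage 1–4 codes cannot simply be dropped.** A reader might think that Renal disease still covers them. It does not: that variable covers 180 days before index and has no Table 3 row.

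**The size is assumed.** This stands. Positive correlation would also shrink the union. In the extreme, where it equals the larger of C and A, prevalence is 30–50% and the ratio 0.30/0.20 = 1.5 to 0.50/0.10 = 5.0. The 133 patients are a count before eligibility, not the analysis cohort.

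**Misclassification is disclosed.** Section 9.9 covers provider coding errors, undeterminable severity and milder events being missed. It does not say that chronic kidney disease is counted as renal failure, and here the error is over-capture.

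**Conclusion.** The concern holds in full for the prevalent adverse event and in weaker form for the incident one. For the baseline variable it is a matter of labelling or reporting. In the ESRD subgroup, classing patients as having renal failure is not wrong in itself; what is unsupported is reading it as something that arose on treatment.

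Under the main assumptions in the working, prevalence as coded is 2.2 to 5.5 times the share with acute or end-stage failure. That comparator still contains end-stage disease, which the fix moves to another row, so the revised adverse event would fall below 10–20% by an amount the protocol does not let one compute. The conclusion also rests on the standard meaning of N17, N18 and the dialysis codes, which the sponsor should confirm.

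The change should be made, but it is not critical: it concerns one event under an exploratory objective and one baseline row under primary Objective 1, with no formal comparisons planned.

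**What to change.** In Annex 2 and Table 3, split Renal failure into two rows:
- **(a) Acute or unspecified renal failure:** N17x and N19x, with R34x if wanted. Report this as the adverse event. Apply the washout to these codes only, so that patients with chronic disease stay at risk for an acute event.
- **(b) Chronic kidney disease, end-stage disease or dialysis:** N18x, T82.4, Z49.02 and Z99.2. Judge prior disease on all available pre-index history, and state that the row is not read as treatment-emergent in the ESRD subgroup.

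In Table 2, keep the window from MM diagnosis and either report the same two rows or relabel the variable as chronic kidney disease or renal failure. Do not rely on the 180-day Renal disease component for the codes moved out.

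The cost is one Annex 2 row divided and one or two table rows added, using claims already held. Version 2.0 already corrected Annex 2 codes by amendment, and the final analysis is planned for 27 February 2026 (Section 6). The reported renal failure percentage will be smaller, and any interim output that used the combined list will not match it.

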Exploratory Obj 1	Other pneumonia ²	Medical claim with an ICD-10 code in the inpatient, non-IP, or pharmacy setting for pneumonia other than adenoviral or cytomegaloviral pneumonia (dichotomous)	Index date to end of follow-up, where follow-up will be based on last dose of elranatamab or teclistamab (e.g., 14 days after last recorded dose or 90 days after last recorded dose).
Exploratory Obj 1	Upper respiratory tract Infection ²	Medical claim with an ICD-10 code in the inpatient, non-IP, or pharmacy setting for upper respiratory tract infection (dichotomous)	Index date to end of follow-up, where follow-up will be based on last dose of elranatamab or teclistamab (e.g., 14 days after last recorded dose or 90 days after last recorded dose).
Exploratory Obj 1	Sepsis ²	Medical claim with an ICD-10 code in the inpatient, non-IP, or pharmacy setting for sepsis (dichotomous)	Index date to end of follow-up, where follow-up will be based on last dose of elranatamab or teclistamab (e.g., 14 days after last recorded dose or 90 days after last recorded dose).
Exploratory Obj 1	Cytomegaloviral infection ²	Medical claim with an ICD-10 code in the inpatient, non-IP, or pharmacy setting for cytomegaloviral infection (dichotomous)	Index date to end of follow-up, where follow- up will be based on last dose of elranatamab or teclistamab (e.g., 14 days after last recorded dose or

			90 days after last recorded dose).
Exploratory Obj 1	PJP ²	Medical claim with an ICD-10 code for PJP (dichotomous)	Index date to end of follow-up, where follow-up will be based on last dose of elranatamab or teclistamab (e.g., 14 days after last recorded dose or 90 days after last recorded dose).
Exploratory Obj 1	Hepatitis C ²	Medical claim with an ICD-10 code in the inpatient, non-IP or pharmacy setting for hepatitis C (dichotomous)	Index date to end of follow-up, where follow-up will be based on last dose of elranatamab or teclistamab (e.g., 14 days after last recorded dose or 90 days after last recorded dose).
Exploratory Obj 1	Hepatitis B ²	Medical claim with an ICD-10 code in the inpatient, non-IP or pharmacy setting for hepatitis B (dichotomous)	Index date to end of follow-up, where follow-up will be based on last dose of elranatamab or teclistamab (e.g., 14 days after last recorded dose or 90 days after last recorded dose).

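### Time to infection onset is not restricted to patients free of the infection before index, so carried-over codes can count as onset near day 0, and its risk window is stated in two different ways

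*Protocol*

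**What the plan says.** In Table 3 (section 9.3) the individual infection rows carry footnote 2: "Variable will be measured as incident and prevalent. Incident cases have 60-day washout period applied". Their assessment period is tied to the last dose ("e.g., 14 days after last recorded dose or 90 days after last recorded dose").

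The row for time to infection onset follows directly. It is defined as "Time in days from index date to first infection for the following infections", with assessment period "Index date until censor", the same entry that OS and TTNT/D have. The list of infections after the colon is not in the text available, so I take the infections to be those in the rows above. The missing list is not a finding.

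Section 9.7.6 sets the exclusion of prior events for one analysis: "For the incidence analysis, only patients who did not have the event prior to their index date will be included". It then gives the assessment periods, "from the index date until 14 days or 90 days after their last administration of the index medication". Time to infection onset comes next as an additional, unadjusted Kaplan-Meier analysis, with the median in days, the IQR and a 95% CI. The closing censoring rule names death, next treatment (CAR-T, BsAbs, bendamustine or belantamab), end of Part A or B coverage, and end of data.

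**The concern.** An infection event here is a claim with an ICD-10 code, and a code records that a condition is being treated or followed, not that it began that day. A patient treated for pneumonia before index and coded again at an early visit has a first infection within days of index. Hepatitis B and C, which have their own infection rows, are more exposed still if they are on the onset list. The protocol recognises this problem by defining a 60-day washout for incident infections, but does not extend it to the analysis that is named onset. The start of the curve is then pulled down and the reported median is too short as a description of when new infections appear.

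The second issue is the time at risk. Table 3 runs this outcome to censoring, while 9.7.6 speaks of 14 or 90 days after the last administration. Two analysts could produce two different curves from the same text, and a reader could not tell whether the curve covers the same infections as the incidence table.

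**Working it through.** The protocol states no expected median, event count or infection rate for this outcome, so there is no figure to reproduce. I made two checks.

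**1. Effect of carried-over codes on the median (illustration)**

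Assumptions, none from the documents: a share q of patients has an infection ongoing at index that is coded again at about day 0, and the rest have exponential onset with rate λ.

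- Survival: S(t) = (1 − q)·exp(−λt)
- Setting S(t) = 1/2: t = [ln 2 + ln(1 − q)]/λ, for q below 0.5
- Incident-only median (q = 0): ln 2/λ
- Ratio: 1 + ln(1 − q)/ln 2, which does not depend on λ

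| q (assumed) | Ratio of medians | If the incident-only median were 90 days |
|---|---|---|
| 5% | 1 − 0.0513/0.6931 = 0.926 | 83 days |
| 10% | 1 − 0.1054/0.6931 = 0.848 | 76 days |
| 20% | 1 − 0.2231/0.6931 = 0.678 | 61 days |
| 30% | 1 − 0.3567/0.6931 = 0.485 | 44 days |

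A simulation with the carried-over code spread over days 0–14, and an assumed rate of 0.08 new infections per month, gives medians of 262, 221 and 178 days for q = 0, 10% and 20%. The ratios are 221/262 = 0.84 and 178/262 = 0.68, in line with the formula.

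**2. How far apart the two risk windows can be (date arithmetic)**

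Inputs: earliest index date 14 August 2023 (section 9.2); end of data December 2025 (section 9.4), taken as 31 December 2025; day 8 and day 168 as the ends of the step-up period and Maintenance Period 1 (Table 4).

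- Index to end of data: 870 days
- Time at risk after the last dose under the open-ended reading: 870 days if the last dose is at index, 870 − 8 = 862 if on day 8, 870 − 168 = 702 if on day 168
- Under the other reading: at most 14 or 90 days

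These are maxima for a patient who is indexed on the first possible day, stays alive and covered, and starts none of the listed next treatments. They show that the two readings differ materially. They do not show how many infections fall in the gap.

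**The case against.** The case on the other side has several parts.

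*Footnotes.* The missing washout marker on the onset row proves little. Superscripts sit on the event names, the list of names for this row is not in the available text, and markers are also absent from rows such as ICANS whose neighbours carry them. This stands, and the point does not rest on the marker. It rests on 9.7.6, which ties the exclusion of prior events to the incidence analysis.

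*Prevalence.* The same infections are also reported as prevalent, without washout, so an unwashed curve has a counterpart in the plan. That is true, but prevalence does not claim to date the start of anything, and a time to onset does.

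*Risk window.* A reader might infer that infections long after stopping are plainly counted as onset on the drug. The documents do not support that. The protocol never calls this outcome on-treatment. The sentence on 14 or 90 days is not confined to prevalence and incidence. The censoring list omits a last-dose limit for those analyses too, although they clearly have one, so its silence settles nothing for this curve. Following patients from initiation until death, next treatment, loss of coverage or end of data is also a defensible descriptive choice. What remains is a conflict between Table 3 and 9.7.6.

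*Size of the late share.* One may be tempted to say that about a third of first infections would fall more than 90 days after the last dose. A simulation with an assumed rate of 0.08 per month, median treatment of 6 months and follow-up of 9–28 months gives 32% (26–37% for rates of 0.12–0.05), but only if nobody is censored at death or next treatment. It is therefore an upper figure for those inputs. If half of treatment stops are death or next treatment (assumed), it falls to 21%; at three quarters, to 13%.

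*Status.* The outcome is exploratory and no formal comparison is planned. That limits the weight of the point but does not remove it, since the median and its CI will be reported as a safety result.

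**Conclusion.** The point holds for the at-risk population. As the text stands, patients whose infection was already being coded before index enter the onset curve and can contribute events near day 0. The bias is towards a shorter median. For assumed carry-over of 5% to 30% the median is reduced by 7% to 51%, with 15% and 32% reductions at 10% and 20%. These figures rest on exponential onset and on carry-over shares that the protocol does not give.

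For the risk window the conclusion is narrower: the two places must be reconciled, and neither is shown to be wrong. The share of first infections beyond 90 days after the last dose cannot be derived from the documents. Only one median is at issue, because incidence in 9.7.6 is a percentage. This is a worthwhile correction to an exploratory safety outcome.

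**What to change.** In Table 3 and section 9.7.6, restrict time to infection onset to patients without that infection in the 60-day pre-index washout, as in the incidence analysis.

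In the same two places, state which risk window applies to this curve. Either show it limited to 90 days after the last administration, with 14 days as the alternative, so that it matches the incidence table; or keep the open-ended period and label the curve as all first infections after initiation, including those after stopping.

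The cost is a clause or two in each place. The washout flags and last-dose dates are already needed for the incidence analysis. The restricted curve will have slightly fewer patients and events, so its confidence interval may widen a little.
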